APPENDIX E - BLOOD SAMPLING SUMMARY

Purpose	Maximum Blood Volume per Sample (mL)	Maximum Number of Blood Samples	Maximum Total Volume (mL)
Hepatitis screen	3.5	1	3.5
Pregnancy tests	3	3	9
Pharmacokinetic sampling	4	12	48
Pharmacodynamic sampling	2	7	14
Haematology	4	7	28
Clinical laboratory tests	3.5	7	24.5
Coagulation	1.8	7	12.6
Anti-drug antibody test	3	5	15
Immunologic analysis	3	1	3
Total			157.6

APPENDIX F - ADVERSE EVENTS

ADVERSE EVENTS

Definition of Adverse Events

An adverse event (AE; or adverse experience) is defined as any untoward medical occurrence experienced by a patient or healthy subject, whether or not considered drug related by the Investigator (or designee). A treatment-emergent AE is an AE that is reported after a dose of study drug.

The following are all AEs:

- unfavourable changes in general condition;
- subjective or objective signs/symptoms;
- concomitant diseases or accidents;
- clinically relevant adverse changes in laboratory parameters observed in a subject during a clinical study.

Adverse events comprise all disturbances of general health status, subjective and objective disease symptoms (including laboratory abnormalities), and accidents observed in the context of a clinical trial, irrespective of a possible causal relationship with the administration of the trial substance. Events occurring in the framework of a clinical trial during drug-free and post-treatment periods, under placebo, or in a reference group receiving drug or nondrug therapy are also to be designated as AEs.

Categorization of Adverse Events

The severity of AEs will be categorized as follows:

- **MILD** = of little concern to the subject and/or of no clinical significance, is not expected to affect the subject's health or well-being;
- **MODERATE** = discomforting enough to cause interference with or change in usual activities, is likely to require medical intervention or close follow-up;
- **SEVERE** = incapacitating or causing inability to work or participate in many or all usual activities, is of concern to the subject or poses substantial risk to the subject's health or well-being, is likely to require medical intervention or close follow-up.

The Investigator (or designee) will make a determination of the relationship of the AE to the study drug using a 4-category system according to the following guidelines:

- **NOT RELATED** = an AE that does not follow a reasonable temporal sequence from administration of the drug and can be reasonably explained by other factors, including underlying disease, complications, concomitant drugs, or concurrent treatment;
- **UNLIKELY RELATED** = an AE that follows a reasonable temporal sequence from the administration of the drug (including after withdrawal of the drug) and cannot be excluded as being possibly caused by the drug (eg, existence of similar reports attributed to the suspected drug and/or its analogues, reactions attributable to the pharmacological effect of the drug), although other factors such as underlying disease, complications, concomitant drugs, or concurrent treatment are presumable;
- **POSSIBLY RELATED** = an AE that follows a reasonable temporal sequence from administration of the drug (including after withdrawal of the drug) and can be excluded as being possibly caused by other factors, such as underlying disease, complications, concomitant drugs, or concurrent treatment;
- **RELATED** = an AE that follows a reasonable temporal sequence from administration of the drug (including after withdrawal of the drug), follows a known or hypothesized cause-effect relationship, and (if appropriate) satisfies the following:
 - positive results obtained in drug sensitivity tests;
 - toxic level of the drug present in blood or other body fluids.

An AE is associated with the use of the drug if there is a reasonable possibility that the experience may have been caused by the drug.

The following categories will be used for the action taken with the study drug for the AE: drug withdrawn, dose not changed, drug interrupted, unknown, and not applicable.

The following categories will be used for the outcome of the AE: resolved, resolved with sequelae, ongoing, fatal, and unknown.

Notification of the Independent Ethics Committees/Institutional Review Boards

Notification of the Independent Ethics Committees/Institutional Review Boards (IECs/IRBs) about all relevant events (eg, serious AEs [SAEs], Suspected Unexpected Serious Adverse Reactions) will be performed by the Sponsor and/or by the Investigator according to all applicable regulations.

Pregnancy

The Investigator must report to the Sponsor any pregnancy occurring in a study subject (or subject's partner) during the subject's participation. The report should be submitted within the same timelines as an SAE, although a pregnancy per se is not considered an SAE. A pregnancy should be followed-up until reporting of the pregnancy's outcome and the birth date.

As information is available, a pregnancy diagnosed during the study will be reported immediately to the Investigator (or designee) or Sponsor, including pregnancy in female partners of male subjects. The pregnancy will be followed to term or outcome and this outcome will be reported to the Sponsor. Pregnancy, in and of itself, is not regarded as an AE or SAE unless the birth results in a congenital anomaly/birth defect or there is suspicion that the study medication may have interfered with the effectiveness of a contraceptive medication or method.

Definition of Serious Adverse Events

An SAE (by Food and Drug Administration [FDA] definition) is any adverse drug experience occurring at any dose that results in any of the following outcomes:

- death;
- a life-threatening adverse drug experience (ie, places the subject, in the view of the Investigator [or designee], at immediate risk of death);
- inpatient hospitalization or prolongation of existing hospitalization;
- a persistent or significant disability/incapacity;
- a congenital anomaly/birth defect;
- important medical event that may require medical or surgical intervention to prevent one of the above outcomes.

Important medical events that may not result in death, be life-threatening, or require hospitalization may be considered SAEs when, based on appropriate medical judgment,

they may jeopardize the patient or subject and may require medical or surgical intervention to prevent one of the outcomes listed in this definition. All SAEs must be collected that occur after the subject signs the Informed Consent Form.

Unexpected Adverse Drug Experience

An unexpected adverse drug experience is any adverse drug experience, the specificity or severity of which is not consistent with the current Investigator's Brochure (IB) or, if an IB is not required or available, the specificity or severity of which is not consistent with the risk information described in the general investigational plan or elsewhere in the current application, as amended.

Reporting

Food and Drug Administration-reportable AEs are AEs that are associated with the use of the drug and are serious and unexpected. Food and Drug Administration-reportable AEs will be reported by the clinical site to the Sponsor, Medical Monitor assigned by the Sponsor, and the responsible IRB/IEC.

The Sponsor and Medical Monitor will be notified in writing (eg, facsimile) within 24 hours of when an AE that is potentially FDA-reportable is first recognized or reported.

Subsequently, a written confirmation or summary of the AE (using FDA Form 3500A, or equivalent) will be sent to the Sponsor within 3 working days of the original notification. (Instructions for completion of FDA Form 3500A may be obtained from the FDA website at www.fda.gov/medwatch/how.htm.)

The IRB/IEC will be notified of any FDA-reportable AE within the timeframe required by the IRB/IEC. The IRB/IEC Serious and Unexpected Adverse Experience Submission Form will be completed and submitted with the copy of the written confirmation or summary of the AE.

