### 4.8.1. Adverse Events

The primary safety endpoint is the proportion of subjects with at least 1 AE comparing individual PTG-100 dose groups with placebo.

Secondary endpoints (all based on comparison of individual PTG-100 dose levels to placebo) will include:

- Frequency and type of AEs (affecting  $\geq 5\%$  of subjects)
- Proportion of subjects with at least 1 SAE
- Number and type of SAEs
- Frequency of adverse events of special interest (AESI) including serious or opportunistic infection (viral, bacterial, fungal including systemic/ gut localization), allergic/ drug reactions, immune system disorders, and PML or new onset neurologic symptoms

Adverse events will be coded using the Medical Dictionary for Regulatory Activities (MedDRA) and displayed in tables and listings using System Organ Class (SOC) and Preferred Term.

Analyses of adverse events will be performed for those events that are considered treatment emergent, where treatment emergent is defined as any adverse event with onset after the administration of study medication through the end of the study visit or any event that was present at baseline but worsened in intensity or was subsequently considered drug-related by the investigator through the end of the study.

Adverse events are summarized by subject incidence rates, therefore, in any tabulation, a subject contributes only once to the count for a given adverse event (SOC or preferred term).

The number and percentage of subjects

- with any treatment-emergent adverse event
- with any treatment-emergent adverse events assessed by the Investigator as related to treatment (definite, probable, or possible relationship)
- with any treatment-emergent serious adverse event
- with treatment-emergent adverse events by severity
- with adverse events affecting  $\geq 5\%$  of subjects within any treatment group across both stages of the study
- with AESI

will be summarized by treatment group and overall. In addition, all active groups will be pooled in the summaries for comparison to placebo. In these tabulations, each subject will contribute

only once (i.e., the most related occurrence or the most intense occurrence) to each of the incidence rates in the descriptive analysis, regardless of the number of episodes.

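### The causality labels in Protocol Appendix F do not fit their definitions and the SAP uses a different scale, so UNLIKELY RELATED events, a mix of suspected and clearly unrelated ones, fall outside the related-TEAE count

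*Protocol*

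**What the plan says.** Protocol Appendix F asks the investigator for a "determination of the relationship of the AE to the study drug using a 4-category system". The levels are:

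- NOT RELATED: the event "does not follow a reasonable temporal sequence from administration of the drug and can be reasonably explained by other factors".
- UNLIKELY RELATED: timing is plausible, and the event "cannot be excluded as being possibly caused by the drug", although other factors may be presumed. The examples given are similar reports for the drug or its analogues, and reactions explained by the drug's pharmacology.
- POSSIBLY RELATED: timing is plausible, and the event "can be excluded as being possibly caused by other factors".
- RELATED: timing is plausible, and the event "follows a known or hypothesized cause-effect relationship", supported where appropriate by a sensitivity test or a toxic drug level.

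Appendix F separately treats an AE as associated with the drug "if there is a reasonable possibility that the experience may have been caused by the drug".

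SAP 4.8.1 counts TEAEs that the investigator judged related, meaning a "definite, probable, or possible relationship". The title of SAP Table 14.3.1.3 names Related as well as the possible, probable and definite levels. Protocol 7.5 commits to summarising TEAEs by relationship and to an AE listing that shows relationship. SAP Section 5 declares no departure from the protocol's analyses.

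**The concern.** A related-AE table is read as the set of events in which the drug is a credible suspect. Here the level whose definition says the drug remains a candidate is labelled UNLIKELY, and the SAP's list of related levels does not include it. The population makes this more than a drafting matter. All subjects have active UC, and Protocol 6.3.2 permits stable oral corticosteroids, azathioprine or 6-MP, and 5-ASA. Underlying disease or another drug can therefore often be presumed as a contributing factor. An opportunistic infection (an AE of special interest) in a subject on azathioprine, where the drug's own pharmacology is also suspected, fits UNLIKELY as worded and so leaves the related table.

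Investigators at roughly 100 to 120 sites must also choose whether to follow the label or the definition. Where they choose differently, the same event gets different codes. The SAP's category names would not reveal this, because they belong to another scale.

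**Working it through.** No arithmetic applies: the plan gives no figure for related events and none can be derived. The check sets the definitions beside the SAP's list.

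| Protocol level | Plausible timing | Other causes | In SAP 4.8.1 list | In Table 14.3.1.3 title |
|---|---|---|---|---|
| NOT RELATED | absent | explain the event | no | no |
| UNLIKELY RELATED | present | presumable; drug not excludable | no | no |
| POSSIBLY RELATED | present | ruled out | yes | yes |
| RELATED | present | no condition stated; cause-effect link needed | not named | yes |
| No protocol level (probable, definite) | – | – | named | named |

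Five things follow.

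1. *Label against definition.* The labels run in the usual order, but the wording under them does not fit. UNLIKELY says the drug stays a candidate. POSSIBLY excludes every other cause, which in that respect is stricter than RELATED.

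2. *Overlap.* UNLIKELY's example of a reaction explained by the drug's pharmacology can also meet RELATED's known or hypothesised link. One event can satisfy both.

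3. *Gap.* NOT RELATED joins its two conditions with an and. An event during treatment with plausible timing and an obvious other cause, such as a UC flare, fails the first condition. The nearest remaining level is UNLIKELY, which therefore mixes suspected reactions with clearly unrelated events.

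4. *Two scales.* The protocol set is {not related, unlikely, possibly, related} and the SAP 4.8.1 set is {possible, probable, definite}. Only possible has a counterpart by name. RELATED enters by way of the table title. Probable and definite would be empty. UNLIKELY is out on every reading, and no mapping is given.

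5. *Where else the events appear.* SAP Tables 14.3.1.1, 14.3.1.2, 14.3.1.4 and 14.3.1.7 cover all TEAEs, and 14.3.1.5 covers serious ones. UNLIKELY events stay in these. None of Tables 14.3.1.1 to 14.3.1.9 is titled as a breakdown by all four relationship levels, so the summary promised in Protocol 7.5 is only partly delivered. Causality enters one other rule: SAP 4.8.1 lets a baseline event become treatment-emergent if it is later judged drug-related. That is a narrow route, since an event that predates dosing would rarely have plausible timing.

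**The case against.** The case against has real force. The Table 14.3.1.3 title does name Related, so with Possibly it already yields the grouping one would want, and probable and definite are merely empty rows. This stands, but it leaves SAP 4.8.1 and its own table in disagreement and does nothing for UNLIKELY.

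The four levels can be read as rising: no timing, timing with other causes, timing without other causes, then a known link. This also stands as a description of the sequence, so it would be wrong to call the levels out of order. The fault is the mismatch of label and definition, with the overlap and gap shown above.

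Three stronger readings are tempting, and the documents do not support them.

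- *Related-AE rates are materially understated in every arm.* Leaving UNLIKELY out does omit some suspected reactions if definitions are followed literally, but nothing shows how many. Counting all of UNLIKELY would overshoot by adding disease events.
- *The comparison with placebo is biased, or the primary safety result is at risk.* Investigators are blinded and use one scale in every arm. The primary safety endpoint is the proportion of subjects with at least one AE, and none of the listed secondary safety endpoints is defined by causality level.
- *The labels suppress expedited reporting.* Appendix F gives reportability its own reasonable-possibility test and does not refer to the four levels. An UNLIKELY event can meet it. What remains is that no text says how the levels relate to that test.

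**Conclusion.** The point holds as a defect in the rule, not as a demonstrated error in a result. Followed as written, the two documents keep every UNLIKELY RELATED event out of the related-TEAE count and Table 14.3.1.3, although the definition of that level says the drug cannot be ruled out, and they provide no planned table in which those events can be seen by relationship. The related table would therefore be hard to interpret in either direction: it omits some suspected reactions, and the omitted level is too mixed simply to be added back.

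The size is unknown. It depends on how many events are coded UNLIKELY and what share of those are suspected reactions, and neither document gives either figure. The conclusion assumes that the CRF uses the protocol's four levels and that investigators apply the definitions rather than the bare labels. If they go by the labels, fewer suspected events are lost, but the coding no longer follows the protocol. The all-TEAE tables, the AE listing promised in Protocol 7.5 and the primary safety endpoint are unaffected. This should be corrected because safety is a primary objective and the correction is cheap.

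**What to change.** Make these changes before unblinding, so that the grouping cannot look data-driven.

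1. Reword Appendix F so that each label fits its definition. An event for which the drug cannot be excluded but other factors are also plausible becomes Possibly related. An event with plausible timing that is clearly better explained by another cause becomes Not related or Unlikely related; state which.
2. Use that single four-level list in the CRF guidance, SAP 4.8.1 and the Table 14.3.1.3 title. Remove probable and definite, and define related as Possibly related plus Related.
3. For events already coded under the current Appendix F wording, add one TEAE table by treatment group and all four relationship levels. This makes the UNLIKELY events visible without counting them all as related, and it meets the Protocol 7.5 commitment.

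The cost is wording changes in Appendix F, the CRF guidance and the SAP, plus one extra table. No new data are needed.

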APPENDIX G - INFLAMMATORY BOWEL DISEASE QUESTIONNAIRE (IBDQ)

INSTRUCTIONS FOR SELF-ADMINISTERED INFLAMMATORY BOWEL DISEASE QUESTIONNAIRE (IBDQ)

This questionnaire is designed to measure the effects of your inflammatory bowel disease on your daily function and quality of life. You will be asked about symptoms you have been having as a result of your bowel disease, the way you have been feeling in general, and how your mood has been.

There are two versions of this questionnaire, the IBDQ and IBDQ-Stoma. If you have a colostomy or ileostomy, you should complete the IBDQ-Stoma. Questions 1, 5, 17, 22, 24 and 26 are slightly different in each version. Be sure you have the correct questionnaire.

On this questionnaire there are 32 questions. Each question has graded response choices numbered from 1 to 7. Please read each question carefully and answer the number which best describes how you have been feeling in the past 2 weeks.

EXAMPLE

How often have you felt unwell as a result of your bowel problem in the past 2 weeks?

- 1 ALL OF THE TIME**
- 2 MOST OF THE TIME**
- 3 A GOOD BIT OF THE TIME**
- 4 SOME OF THE TIME**
- 5 A LITTLE OF THE TIME**
- 6 HARDLY ANY OF THE TIME**
- 7 NONE OF THE TIME**

If you are having trouble understanding a question, **STOP** for a moment! Think about what the question means to you. How is it affected by your bowel problem? Then answer the question as best you can. You will have the chance to ask the research assistant questions after completing the questionnaire. This takes only a few minutes to complete.

QUALITY OF LIFE IN INFLAMMATORY BOWEL DISEASE QUESTIONNAIRE (IBDQ)

This questionnaire is designed to find out how you have been feeling during the last 2 weeks. You will be asked about symptoms you have been having as a result of your inflammatory bowel disease, the way you have been feeling in general, and how your mood has been.

1. How frequent have your bowel movements been during the last two weeks? Please indicate how frequent your bowel movements have been during the last two weeks by picking one of the options from

- 1 BOWEL MOVEMENTS THE MOST FREQUENT YOU HAVE EVER EXPERIENCED
- 2 EXTREMELY FREQUENT
- 3 VERY FREQUENT
- 4 MODERATE INCREASE IN FREQUENCY OF BOWEL MOVEMENTS
- 5 SOME INCREASE IN FREQUENCY OF BOWEL MOVEMENTS
- 6 SLIGHT INCREASE IN FREQUENCY OF BOWEL MOVEMENTS
- 7 NORMAL, NO INCREASE IN FREQUENCY OF BOWEL MOVEMENTS

2. How often has the feeling of fatigue or of being tired and worn out been a problem for you during the last 2 weeks? Please indicate how often the feeling of fatigue or tiredness has been a problem for you during the last 2 weeks by picking one of the options from

- 1 ALL OF THE TIME
- 2 MOST OF THE TIME
- 3 A GOOD BIT OF THE TIME
- 4 SOME OF THE TIME
- 5 A LITTLE OF THE TIME
- 6 HARDLY ANY OF THE TIME
- 7 NONE OF THE TIME

3. How often during the last 2 weeks have you felt frustrated, impatient or restless? Please choose an option from

- 1 ALL OF THE TIME
- 2 MOST OF THE TIME

- 3 A GOOD BIT OF THE TIME
- 4 SOME OF THE TIME
- 5 A LITTLE OF THE TIME
- 6 HARDLY ANY OF THE TIME
- 7 NONE OF THE TIME

4. How often during the last 2 weeks have you been unable to attend school or do your work because of your bowel problem? Please choose an option from

- 1 ALL OF THE TIME
- 2 MOST OF THE TIME
- 3 A GOOD BIT OF THE TIME
- 4 SOME OF THE TIME
- 5 A LITTLE OF THE TIME
- 6 HARDLY ANY OF THE TIME
- 7 NONE OF THE TIME

5. How much of the time during the last 2 weeks have your bowel movements been loose? Please choose an option from

- 1 ALL OF THE TIME
- 2 MOST OF THE TIME
- 3 A GOOD BIT OF THE TIME
- 4 SOME OF THE TIME
- 5 A LITTLE OF THE TIME
- 6 HARDLY ANY OF THE TIME
- 7 NONE OF THE TIME

6. How much energy have you had during the last 2 weeks? Please choose an option from

- 1 NO ENERGY AT ALL
- 2 VERY LITTLE ENERGY
- 3 A LITTLE ENERGY
- 4 SOME ENERGY
- 5 A MODERATE AMOUNT OF ENERGY
- 6 A LOT OF ENERGY
- 7 FULL OF ENERGY

7. How often during the last 2 weeks did you feel worried about the possibility of needing to have surgery because of your bowel problem? Please choose an option from

- 1 ALL OF THE TIME
- 2 MOST OF THE TIME
- 3 A GOOD BIT OF THE TIME
- 4 SOME OF THE TIME
- 5 A LITTLE OF THE TIME
- 6 HARDLY ANY OF THE TIME
- 7 NONE OF THE TIME

8. How often during the last 2 weeks have you had to delay or cancel a social engagement because of your bowel problem? Please choose an option from

- 1 ALL OF THE TIME
- 2 MOST OF THE TIME
- 3 A GOOD BIT OF THE TIME
- 4 SOME OF THE TIME
- 5 A LITTLE OF THE TIME
- 6 HARDLY ANY OF THE TIME
- 7 NONE OF THE TIME

9. How often during the last 2 weeks have you been troubled by cramps in your abdomen? Please choose an option from

- 1 ALL OF THE TIME
- 2 MOST OF THE TIME
- 3 A GOOD BIT OF THE TIME
- 4 SOME OF THE TIME
- 5 A LITTLE OF THE TIME
- 6 HARDLY ANY OF THE TIME
- 7 NONE OF THE TIME

10. How often during the last 2 weeks have you felt generally unwell? Please choose an option from

- 1 ALL OF THE TIME
- 2 MOST OF THE TIME

- 3 A GOOD BIT OF THE TIME
- 4 SOME OF THE TIME
- 5 A LITTLE OF THE TIME
- 6 HARDLY ANY OF THE TIME
- 7 NONE OF THE TIME

11. How often during the last 2 weeks have you been troubled because of fear of not finding a toilet? Please choose an option from

- 1 ALL OF THE TIME
- 2 MOST OF THE TIME
- 3 A GOOD BIT OF THE TIME
- 4 SOME OF THE TIME
- 5 A LITTLE OF THE TIME
- 6 HARDLY ANY OF THE TIME
- 7 NONE OF THE TIME

12. How much difficulty have you had, as a result of your bowel problems, doing leisure or sports activities you would have liked to have done during the last 2 weeks? Please choose an option from

- 1 A GREAT DEAL OF DIFFICULTY; ACTIVITIES MADE IMPOSSIBLE
- 2 A LOT OF DIFFICULTY
- 3 A FAIR BIT OF DIFFICULTY
- 4 SOME DIFFICULTY
- 5 A LITTLE DIFFICULTY
- 6 HARDLY ANY DIFFICULTY
- 7 NO DIFFICULTY; THE BOWEL PROBLEMS DID NOT LIMIT SPORTS OR LEISURE ACTIVITIES

13. How often during the last 2 weeks have you been troubled by pain in the abdomen? Please choose an option from

- 1 ALL OF THE TIME
- 2 MOST OF THE TIME
- 3 A GOOD BIT OF THE TIME
- 4 SOME OF THE TIME
- 5 A LITTLE OF THE TIME
- 6 HARDLY ANY OF THE TIME

